8.3.6 Non-Serious Adverse Events of Special Interest

NSAESIs are required to be reported by the Investigator to the Sponsor immediately (i.e., no more than 24 hours after learning of the event ([Appendix 2](#) for reporting instructions).

NSAESIs of special interest for this study include the following:

- Cases of an elevated ALT or AST in combination with either an elevated bilirubin or clinical jaundice, as defined in [Appendix 3](#).
- Suspected transmission of an infectious agent by the study treatment, as defined below:

Any organism, virus, or infectious particle (e.g., prion protein transmitting transmissible spongiform encephalopathy), pathogenic or non-pathogenic, is considered an infectious agent.

Transmission of an infectious agent may be suspected from clinical symptoms or laboratory findings that indicate an infection in a participant exposed to a medicinal product. This term applies only when a contamination of the study treatment is suspected.

8.3.7 Disease-Related Events and/or Disease-Related Outcomes Not Qualifying as AEs or SAEs

No disease-related events are expected for this study.

8.3.8 Management of Specific Adverse Events

Guidelines for the management of participants who experience specific AEs to the IMPs other than RO7172508 (obinutuzumab and tocilizumab) are provided in the obinutuzumab and tocilizumab Investigator's Brochure and local prescribing information. Guidelines for the management of participants who experience AEs associated with RO7172508 are provided in [Table 17](#), [Table 18](#), and [Table 19](#). For cases in which management guidelines are not covered in this protocol or in the obinutuzumab/tocilizumab Investigator's Brochure and local prescribing information, toxicities should be treated as deemed appropriate by the Investigator according to best medical judgment and local medical guidelines. Please see the [RO7172508 Investigator's Brochure](#) for further details of the safety profile.

8.3.8.1 Infusion-Related Reactions/Cytokine Release Syndrome

Administration of RO7172508 may cause a spectrum of infusion-related adverse events that typically occur during, shortly after, or within 24 hours after the infusion and could be associated with an IRR or CRS.

IRRs are typically seen with the first two cycles and without symptoms of hypoxia and/or hypotension. In contrast, CRS is more likely to occur with the symptoms of hypoxia and/or hypotension at any cycle and with any symptom following from the third cycle onward. IRR events are therefore defined as taking place in association with the first two infusions and without symptoms of hypotension and/or hypoxia.

Given the overlap in signs and symptoms, IRRs may be indistinguishable from CRS, defined as a disorder characterized by nausea, headache, tachycardia, hypotension, rash, shortness of breath, and renal, coagulation, hepatic, and neurologic disorders ([Lee et al. 2014](#)). Severe CRS may be associated with other clinical sequelae, such as disseminated intravascular coagulation and capillary leak syndrome.

Given that IRRs may be indistinguishable from CRS based on symptomatology, single-treatment management guidelines are being recommended for both IRRs and CRS, during or up to 24 hours after infusion of RO7172508. The approach to have single-treatment management guidelines for IRR and CRS will continue to be reviewed as additional safety data accumulate.

[Table 17](#) provides guidelines for management of infusion-related reactions/ cytokine release syndrome.

Table 17 Recommendations for Management of IRRs and CRS considered related to RO7172508^a

Symptoms	Guidance

Grade 1 Fever, constitutional symptoms
	
 – If RO7172508 infusion is ongoing, slow infusion to ≤50% or interrupt infusion – Symptomatic treatment and supportive care – Monitor fluid balance and administer IV fluids as clinically indicated – At next cycle administer pre-medications that may include antihistamine, antipyretics/NSAIDs, antiemetic, and corticosteroids (See Table 14 and Table 15)

Grade 2 Hypotension: responds to fluids
 
OR
 
Hypoxia*: requires <40% FiO₂ (or ≤5 L/min of 100% O₂) to maintain adequate hemoglobin oxygen saturation
	
 – Follow all Grade 1 recommendations – Hold further RO7172508 treatment until symptoms completely resolved – At the restart of the infusion, slow down the rate of infusion to 25% of original rate – If event occurred during infusion, and symptoms recur with the same or greater severity following interruption of RO7172508 infusion, the infusion must be stopped immediately. Consider to manage as a Grade 3 event. No further RO7172508 will be administered for the cycle – Monitor cardiac and other organ functions closely – Hemodynamic support as indicated and oxygen for hypoxia – Admit to ICU as appropriate – Consider administering a single dose of tocilizumab IV 8 mg/kg – If no improvement within 24 hours: 
 a) Notify Medical Monitor b) Administer IV corticosteroids (e.g., methylprednisolone [2 mg/kg/day] or dexamethasone 10 mg if neurologic symptoms are present) – Additional monitoring and evaluation: 
 – Consider 24 hour hospitalization – Work up for organ functions (e.g. liver, cardiac) based on clinical assessment of the Investigator – May receive RO7172508 in next cycle if symptoms resolve to Grade ≤1 with the approval of the Medical Monitor including considerations for dose reduction and/or reduction of infusion rate at the next administration. – At next cycle administer pre-medications that may include antihistamine, antipyretics/NSAIDs, antiemetic, and corticosteroids

Table 17 Recommendations for Management of IRRs and CRS considered related to RO7172508^a (cont.)


Grade 3 Hypotension: requires vasopressor support
 
OR
 
Hypoxia*: requires >40 % FiO₂ or >5 L/min O₂ to maintain adequate hemoglobin oxygen saturation
	
 – If RO7172508 infusion is ongoing, stop infusion immediately – No further RO7172508 will be administered for the cycle – Cardiopulmonary and organ function monitoring in ICU – Closely monitor and maintain fluid balance; and other supportive care as clinically indicated – Vasopressor support for hypotension with high and repeated doses if required – Notify Medical Monitor – Initiate IV corticosteroids (e.g., methylprednisolone [2 mg/kg/day] or dexamethasone 10 mg if neurologic symptoms are present) – Administer tocilizumab 8 mg/kg IV 
 – If no clinical improvement within 24 h: repeat dose of tocilizumab 8 mg/kg – Additional monitoring and evaluation: 
 – Hospitalize patient for 24 hours – Work up for organ functions (e.g. liver, cardiac) based on clinical assessment of the Investigator – Permanently discontinue RO7172508 and follow the Schedule of Assessments (Table 5)

Grade 4 Hypoxia: Mechanical ventilation required
	
 – Follow all Grade 3 guidelines – Permanently discontinue RO7172508

^a Grading of events is based on CTCAE V5.0

* Isolated hypoxia (without hemodynamic instability) requiring oxygen support in a patient with tumor (primary or metastatic) in the lung should be managed as per tumor inflammation guidelines (Table 18) and not per CRS guidelines (Table 17).

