During the course of this study, the need for obinutuzumab pretreatment will be assessed based on loss of RO7172508 exposure and/or ADA-related safety events. Details, including decision criteria, are provided in Section 4.1.3 and Appendix 9. If on-target toxicity is reported predominantly in the first cycle of treatment, fractionated dosing may be implemented for the first cycle to improve tolerability. RO7172508 treatment would start with 10% of the planned dose on Cycle 1 Day 1, 30% of the planned dose on Cycle 1 Day 8 and 60% of the planned target dose on Cycle 1 Day 15, followed by the full dose treatment from Cycle 2 Day 1 onwards as described in Figure 2. By using a step-up fractionated dosing approach, it is predicted that the lower peak exposures (C_{max}) will result in lower cytokine levels to that when the full dose is given on Day 1. The fractionated dosing regimen may be adjusted depending on emerging data and in discussion with the Investigators. A similar approach to increase the dose administered during the first three weeks as applied with dose-fractionation in the Q3W treatment group, may also be employed in the once weekly (QW) treatment group. If a patient in the fractionated dose cohort experiences any adverse event that results in a delay of the next administration of RO7172508 beyond one week, the dose at which the treatment should be restarted will require agreement between the investigator and the Sponsor.

Figure 2 Fractionated Dosing Design for Q3W and QW

At least 3 evaluable participants will be treated in each cohort during the IV or SC dose-escalation regimen.

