7.1 DISCONTINUATION OF STUDY TREATMENT

See the SoA (Section [1.3](#) for data to be collected at the time of treatment discontinuation and follow-up and for any further evaluations that need to be completed.

Participant must discontinue study treatment if they experience any of the following:

- Pregnancy
- Grade 3 IRR/CRS for RO7172508
- IgE-mediated hypersensitivity reactions, including anaphylaxis.
- Any toxicity which is not manageable with dose-delays (as allowed per protocol), dose-decrease and/or appropriate treatment.
- Symptomatic disease progression when there is a consensus that the participant will not benefit from study treatment.
- If a patient develops alanine aminotransferase or aspartate aminotransferase increase > 10x ULN associated with the 3rd infusion of RO7172508 or later.

Participants who discontinue study treatment prematurely will be asked to return to the clinic for an End-of-Treatment visit (see Section [8.10.3](#)) and may undergo follow-up assessments (see Section [8.10.4](#)). The primary reason for premature study treatment discontinuation should be documented on the appropriate eCRF. Participants who discontinue study treatment prematurely may be replaced for the following reasons to ensure adequate numbers of evaluable participants:

- Participant who withdraws from the study prior to the treatment start may be replaced.
- Participants who fail to complete their DLT assessment period because of non-drug-related reasons.
- In the case of a major protocol violation when participants are excluded from Cycle 1 of treatment (these participants will be excluded from the MTD/DLT analysis

but might continue the treatment if deemed beneficial and according to clinical judgment).

- Cohorts may be expanded to acquire additional paired tumor biopsies.

Participants will be treated for 24 months (the treatment period may be modified if supported by emerging data) or until disease progression, loss of clinical benefit, unacceptable toxicities, or withdrawal from treatment for other reasons or death.

As with other immunotherapies, treatment beyond RECIST ([Appendix 6](#)) progression could be considered. The criteria below will be needed to continue treatment beyond initial apparent progressive disease per RECIST v1.1 (e.g., radiological progression secondary to tumor inflammation):

- Absence of clinical deterioration and Investigator–assessed potential clinical benefit for the participant and

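### IRR is defined by infusion count but explained by cycle count, and the ALT/AST stop also counts infusions, so IRR coding and this discontinuation rule work differently under fractionated (and possibly weekly SC) dosing than under Q3W

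*Combined protocol and SAP*

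**What the plan says.** Section 8.3.8.1 gives the timing of the two reactions by cycle. For IRR: "IRRs are typically seen with the first two cycles and without symptoms of hypoxia and/or hypotension". CRS is described as more likely with hypoxia or hypotension at any cycle, and "with any symptom following from the third cycle onward". The next sentence draws a definition from this but changes the unit: "IRR events are therefore defined as taking place in association with the first two infusions and without symptoms of hypotension and/or hypoxia".

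Section 7.1 opens its list with "Participant must discontinue study treatment if they experience any of the following" and includes this item: "If a patient develops alanine aminotransferase or aspartate aminotransferase increase > 10x ULN associated with the 3rd infusion of RO7172508 or later". Section 8.3.8.3 uses a third-dose threshold for GI referral in diarrhea, but counts administrations.

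The schedules are in Section 4.1, Section 4.1.2.2 and the schedules of activities. For fractionated IV dosing, "RO7172508 treatment would start with 10% of the planned dose on Cycle 1 Day 1, 30% of the planned dose on Cycle 1 Day 8", then "60% of the planned target dose on Cycle 1 Day 15", with the full dose from Cycle 2 Day 1. SC QW dosing is given three times per 21-day cycle. None of Sections 8.3.8.1, 7.1 and 8.3.8.3 says how its count applies to fractionated, weekly or SC dosing.

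**The concern.** The definition of IRR is presented as following from the cycle-based description, which is only true if infusion number equals cycle number. The plan itself provides for schedules where it does not. A label that depends on how many doses have been given then varies by schedule for clinically identical events.

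This matters because the incidence and nature of AEs are a primary endpoint. Appendix 3 Section 1.1 records reactions within 24 hours as a diagnosis, Table 23 summarizes AEs by mapped term, and Section 9.4 summarizes by cohort and regimen and lists tolerability and safety among the endpoints that may inform the choice of route. Fractionation is introduced to improve first-cycle tolerability, so a reader will naturally compare IRR and CRS rates between fractionated and non-fractionated cohorts. A count-based liver-enzyme stop likewise makes discontinuation rates under that rule depend on schedule.

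**Working it through.** **Inputs.** Cycle length 21 days (schedules of activities); fractionated doses of 10%, 30% and 60% on Days 1, 8 and 15 of Cycle 1, then full dose from C2D1 (Section 4.1); SC QW on Days 1, 8 and 15 of every cycle (Table 3); DLT window of 21 days for Part II Q3W and 42 days for fractionated dosing without delay (Section 4.1.2.2).

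**The plan's own figure.** For a 400 mg target: 0.10 × 400 = 40 mg, 0.30 × 400 = 120 mg, 0.60 × 400 = 240 mg. This matches the example in Section 4.3.1.

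**Timing.** Study day = 21 × (cycle − 1) + cycle day.

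| | IV Q3W | IV fractionated | SC QW |
|---|---|---|---|
| Third dose | C3D1: 21 × 2 + 1 = Day 43 | C1D15: 21 × 0 + 15 = Day 15 | C1D15: Day 15 |
| First full dose | dose 1, Day 1 | dose 4, C2D1: 21 × 1 + 1 = Day 22 | dose 1, Day 1 |
| Doses in Cycles 1-2 | 1 + 1 = 2 | 3 + 1 = 4 | 3 + 3 = 6 |
| Of these, beyond the second | 2 − 2 = 0 | 4 − 2 = 2 | 6 − 2 = 4* |

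*Only if an SC injection is read as an infusion. Read literally, the IRR definition does not address SC dosing.

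Counted by cycle, the boundary (C3D1) is Day 43 in all three schedules.

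**IRR label.** Take a reaction with several symptoms but no hypotension or hypoxia. At C1D15 or C2D1 of fractionated dosing it follows infusion 3 or 4, so it is outside the IRR definition, although it lies in the cycles where the text places IRRs. In Cycles 1-2 of Q3W it follows infusion 1 or 2 and meets the definition.

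**ALT/AST stop.** The criterion can first be met at infusion 3.
- Q3W: Day 43, after 2 × 100% = 200% of one target dose, and after the 21-day DLT window has closed.
- Fractionated: Day 15, when 10% + 30% = 40% of one target dose has been given before that infusion, and inside the 42-day window.

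The same rise above 10 times ULN after the first full dose does not meet this criterion in Q3W (infusion 1) but does in fractionated dosing (infusion 4).

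**The case against.** The case against gives the point narrower limits, and much of it stands.

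- A reader might infer that a fever-only reaction falls between the two labels. It does not: Section 6.1.1 has an IRR-like reaction with one isolated symptom reported as its own AE. Only reactions with several symptoms are affected.
- A reader might infer that third and later infusions become CRS by definition. The cycle wording for CRS is descriptive, and CRS is otherwise characterized by symptoms without a cycle limit. These events are excluded from IRR; the text does not settle what they are called instead.
- A reader might infer that the label leads to more discontinuations. It does not: IRR and CRS share Table 17 and a single Grade 3 stop in Section 7.1. The DLT criteria in Section 4.1.3.1 are grade-based and name neither, so the MTD is not affected by the label.
- Section 7.1 does not contradict itself. It uses one count throughout, and for IV dosing infusions and administrations are the same thing. Counting exposures may be deliberate; the documents give no reason either way. Table 18 also has a liver-enzyme stop that does not depend on schedule (Grade 3 or higher lasting 5 days or more), though it allows exceptions and does not replace the Section 7.1 rule.
- It is tempting to turn the dose counts into a share of participants by assuming a constant reaction risk per dose. The documents give no such risk. Section 4.2.1 reports that cibisatamab toxicity came mainly in the first days after the initial dose, and Section 4.1 expects lower cytokine levels with step-up dosing.
- Fractionation is optional, analyses are descriptive, and route selection weighs several kinds of data, so a biased choice of schedule is a possibility and not a demonstrated result.

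None of this removes the change of unit within Section 8.3.8.1, or the missing statement of how any of the three counts applies outside non-fractionated Q3W dosing.

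**Conclusion.** The point holds in two parts.

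First, the IRR definition uses a unit that does not follow from its stated basis. The gap is 0 of 2 doses in Cycles 1-2 for Q3W and 2 of 4 for fractionated IV dosing. For SC QW it is 4 of 6 on the reading that infusion means administration, and undefined otherwise. These counts are exact given the planned schedule without delays; how many events they affect cannot be estimated from the documents. The consequence is limited to AE coding and to comparisons of separate IRR and CRS rates between schedules or routes.

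Second, the mandatory ALT/AST stop begins 43 − 15 = 28 days earlier in fractionated dosing than in Q3W, before the first full dose and inside the DLT window, and its application to SC dosing is unclear. Discontinuation rates under this rule are therefore not comparable across schedules.

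**What to change.** Reconcile the counting unit in Sections 8.3.8.1, 7.1 and 8.3.8.3, and state for each schedule (Q3W, fractionated, QW) and route (IV, SC) how the count applies. Which clinical threshold is right is for the sponsor and investigators; no rule is proposed here.

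In Table 23, specify that comparisons between schedules or routes use the combined IRR/CRS rate, tabulated by dose number and by cycle. Appendix 3 Section 1.1 already collects signs and symptoms on one joint IRR/CRS eCRF, so the combined rate needs no new data collection. When discontinuations are compared, note that those under the ALT/AST rule depend on schedule.

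Cost: protocol wording and one additional table.

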8.3.8.2 Suspected Tumor Inflammation

Adverse events associated with tumor inflammation have been reported with T-cell engaging therapies and are consistent with the mechanism of action of such therapies that lead to influx of T-cells into tumor sites. Tumor inflammation is driven by influx of T cells and it is dependent on the mechanism of action of RO7172508. Along with the volume increase dependent on the influx of T cells, there may be an additional volumetric component possibly dependent by local inflammation. Events involving tumor inflammation, including tumor flare, have been reported in studies with in-class agent cibusatamab. These events tend to occur with a short time to onset following administration and may present with varying degrees of severity.

In addition, depending on tumor size and anatomic location, events associated with tumor inflammation may potentially result in mass effects on vital structures, including airways, major blood vessels, and/or major organs. Depending on the nature of the tumor inflammation, further medical and/or surgical management may be necessary (e.g. anti-inflammatory agents, airway management, decompression, cardiac function monitoring in terms of ejection fraction). Participants with tumors involving critical anatomic locations should be closely monitored for tumor inflammation and prospective consideration for preventive or interventional measures may need to be considered or planned prior to dosing. The treating physician/study investigator should contact the Medical Monitor to discuss risk assessment and mitigation strategies prior to initiating RO7172508 treatment in case participants present disease close to vital structures.

For further safety information, refer to the [RO7172508 Investigator Brochure](#).

Table 18 provides guidelines for management of suspected tumor inflammation.

If corticosteroids are administered, taper before stopping treatment. In case of concurrent respiratory and other organ toxicities, follow the management recommendations for respiratory toxicities.

Table 18 Management of Suspected Tumor Inflammation

Event	Initial Management Recommendation	Action to be Taken with RO7172508
Respiratory toxicities		
Supportive measures, e.g., oxygen support and intubation, as indicated.		
Grade 1	Monitor participant closely.	Continue treatment.
Grade 2	Monitor participant closely. If no resolution to Grade \leq 1 within 48 hours, administer 1 mg/kg/day of IV methylprednisolone or equivalent followed by tapering with oral steroids until Grade \leq 1.	Hold until resolution to Grade \leq 1.
Grade 3	Administer 2 mg/kg/day of IV methylprednisolone or equivalent followed by tapering with oral steroids until resolution to Grade 1 or baseline.	Hold until resolution to Grade \leq 1.
Grade 4	Ensure participant access to an intensive care unit is available	Consider permanent discontinuation after discussion with Medical Monitor.

Table 18 Management of Suspected Tumor Inflammation (cont.)

Toxicities in other organs systems		
Grade 1 or 2	Monitor participant closely	Continue if Grade 1 event (for Grade 2 events, hold until resolution to Grade 1).
Grade 3	Administer 1 mg/kg/day of IV methylprednisolone or equivalent followed by tapering with oral steroids until Grade 1 or baseline (consider escalating next day to 2 mg/kg/day if no improvement, or escalate to 2 mg/kg directly if event occurs during prophylactic treatment with steroids). Ensure participant access to an intensive care unit is available.	Hold until resolution to Grade ≤ 1. For grade ≥ 3 toxicity and duration ≥ 5 days permanent discontinuation (including liver enzyme elevations). Exceptions may be warranted after discussion of benefit/risk profile of a specific patient with Medical Monitor
Grade 4	Administer 2 mg/kg/day of IV methylprednisolone or equivalent until Grade 1 or better. Ensure participant access to an intensive care unit is available.	

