4.1.3.1 Dose-Limiting Toxicities

For the purpose of this study, a DLT will be defined as *any of the following events occurring during the DLT window and not attributable to underlying disease or intercurrent illness*:

- Hematological toxicities defined as:
 - Grade 4 neutropenia (i.e., absolute neutrophil count [ANC] < 0.5×10^9 cells/L for a minimal duration of one week).
 - Grade 3 and 4 febrile neutropenia.
 - Grade 4 thrombocytopenia lasting > 48 hours
 - Grade 3 thrombocytopenia associated with bleeding episodes.

- Grade ≥ 3 non-hematological toxicity with the following exceptions:
 - Alopecia (any grade)
 - Grade 3 nausea or vomiting that resolves to Grade ≤ 1 with or without supportive therapy within one week.
 - Grade 3 hypophosphatemia and transient Grade 3 hyperbilirubinemia resolved within one week.
 - Grade ≥ 3 fatigue that resolves to Grade ≤ 2 within one week.
 - Fever $> 40^{\circ}\text{C}$ (i.e., Grade 3) that occurs within 48 hours of RO7172508 infusion and improves to $\leq 40^{\circ}\text{C}$ (Grade ≤ 2) within 48 hours and fully resolves within one week.
 - Grade 3 arthralgia that can be adequately managed with supportive care or that improves/resolves to Grade ≤ 2 within one week.
 - Grade 3 diarrhea, colitis, enteritis that resolves to Grade ≤ 1 within one week with no fever or dehydration.
 - Laboratory values of Grade ≥ 3 that are judged not clinically significant by the Investigator.
 - Grade 3 tumor pain that starts within 24 hours of infusion and improves/resolves to Grade ≤ 2 within one week.
 - Grade 3 hypoxia that starts within 24 hours of infusion and improves/resolves to Grade ≤ 2 within one week.
 - In participants with lung lesions, Grade 3 transient dyspnea secondary to localized lung edema that starts within 24 hours of infusion and resolves to Grade 1 or baseline within one week, and transient bronchospasm that resolves within 24 hours.
 - In participants with liver lesions, Grade 3 transient increase of bilirubin, transaminases (aspartate aminotransferase [AST]/alanine aminotransferase [ALT]) and/or gamma-glutamyl transferase (GGT) that starts within 24 hours of infusion and recovers to Grade 1 or baseline within one week.

Failure to recover from any RO7172508-related toxicity that results in a dose-delay of more than 14 days (any regimen) is defined as a DLT.

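### The rule for concurrent respiratory and other-organ toxicities (8.3.8.2) has no grade condition and conflicts with Table 18 when the other-organ toxicity is the more severe

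*Combined protocol and SAP*

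**What the plan says.** Section 8.3.8.2 introduces the table with "Table 18 provides guidelines for management of suspected tumor inflammation" and, after a sentence on tapering corticosteroids, adds: "In case of concurrent respiratory and other organ toxicities, follow the management recommendations for respiratory toxicities".

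Table 18 has two instruction columns, one for initial management and one for action with RO7172508. It has separate blocks for respiratory toxicities and for other organ systems.

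- **Respiratory, action with RO7172508:** Grade 1 is "Continue treatment". Grades 2 and 3 are a hold until Grade 1 or lower, with no duration limit. Grade 4 is "Consider permanent discontinuation after discussion with Medical Monitor".
- **Other organs, action with RO7172508:** Grade 1 continues and Grade 2 is held until Grade 1. Grade 3 is held until Grade 1 or lower, with the addition "For grade ≥ 3 toxicity and duration ≥ 5 days permanent discontinuation (including liver enzyme elevations", and then "Exceptions may be warranted after discussion of benefit/risk profile of a specific patient with Medical Monitor". The Grade 4 action cell is empty in the text available. Because the clause refers to Grade 3 and above, it is read here as one cell covering Grades 3 and 4, and not as an omission.
- **Respiratory, initial management:** Grade 1 is monitoring. Grade 2 is monitoring, with methylprednisolone 1 mg/kg/day if the event has not come down to Grade 1 within 48 hours. Grade 3 is 2 mg/kg/day.
- **Other organs, initial management:** Grades 1 and 2 are monitoring. Grade 3 is 1 mg/kg/day with possible escalation to 2 mg/kg/day, and Grade 4 is 2 mg/kg/day.

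**The concern.** A precedence rule between two blocks of a table works as intended only if the block that wins is at least as cautious as the one that loses, or if the rule says what happens when it is not. Here the sentence always selects the respiratory block, whatever the two grades are. When the respiratory event is mild and the other-organ event is severe, following the sentence relaxes the instruction for the severe event. Having a second toxicity then leads to less action than having one.

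This is a safety instruction in a first-in-human study of a T-cell engager. Section 2.3 lists dyspnea, hypoxia and raised liver enzymes together as expected consequences of tumor inflammation, so the combination is foreseeable. Investigators at different sites could read the sentence differently and act differently on the same patient.

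**Working it through.** No formula applies. The check sets the sentence against each pair of grades in Table 18, under the two readings that the wording allows.

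**Reading A: the sentence governs both columns.** Each cell compares the action on RO7172508 under the sentence with the action Table 18 gives for the other-organ event alone.

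| Respiratory grade (its action) | Other G1 (alone: continue) | Other G2 (alone: hold) | Other G3 (alone: hold; stop at ≥5 days) | Other G4 (alone: as G3) |
|---|---|---|---|---|
| G1 (continue) | same | hold lost | hold and stop lost | hold and stop lost |
| G2 (hold) | stricter | same | stop lost if ≥5 days | stop lost if ≥5 days |
| G3 (hold) | stricter | same | stop lost if ≥5 days | stop lost if ≥5 days |

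Less restrictive without any condition: 3 cells (respiratory Grade 1 with other-organ Grade 2, 3 or 4). Less restrictive only if the Grade ≥3 event lasts at least 5 days: 2 + 2 = 4 cells, in all of which a hold remains. Total: 3 + 4 = 7 of 12.

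With respiratory Grade 4, the permanent stop for other-organ Grade 3 or 4 at 5 days or more weakens to "Consider permanent discontinuation after discussion with Medical Monitor". That is 2 further combinations, outside the 12.

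As an illustration, take a Grade 3 ALT elevation lasting 6 days and attributed to tumor inflammation. Alone, it meets the permanent-stop clause, subject to a Medical Monitor exception. With a concurrent Grade 1 dyspnea, also attributed to tumor inflammation, the governing row is respiratory Grade 1: "Continue treatment".

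**Reading B: the sentence governs only the initial-management column.** Holds and stops are untouched, so the count of weakened actions on RO7172508 is 0. In the management column:

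- Respiratory Grade 1 with other-organ Grade 3 or 4: monitoring displaces IV steroids (2 combinations).
- Respiratory Grade 2 with other-organ Grade 3 or 4: steroids wait for 48 hours without resolution (2 combinations).
- Respiratory Grade 3 with other-organ Grade 3: the respiratory steroid instruction is the stronger one (2 against 1 mg/kg/day). With other-organ Grade 4 the two are equal at 2 mg/kg/day.

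So 2 + 2 = 4 of the same 12 combinations are weakened under Reading B, all of them with the other-organ event at the higher grade.

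**Search for a tie-break or override.**

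- Section 6.6 accepts a delay of up to two cycles for a non-hematological toxicity to reach Grade 1 or lower. It withdraws the participant if treatment cannot resume after two omitted doses, unless clinical benefit is agreed. The delay is permitted, not required.
- Section 7.1 forces a stop for toxicity that cannot be managed by delay, reduction or treatment, and for ALT or AST above 10 × ULN associated with the third or later infusion.
- Section 8 sends immediate safety concerns to the Sponsor to decide on continuation.
- Table 19 has its own holds and a Grade 4 stop for diarrhea and colitis.

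None of these contains the 5-day rule, and none says that the higher grade or the stricter action governs.

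**The case against.** The best defence is Reading B. The disputed sentence nearly repeats the header of the initial-management column and directly follows a sentence on steroid tapering. At equal Grade 2 or Grade 3 the respiratory steroid instruction is the stronger, which suggests that the sentence was meant to escalate steroid treatment and not to relax anything. Table 18 is also described as guidelines, and the 5-day stop allows exceptions even when it stands alone.

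Much of this stands. It is enough to say that displacement of the hold or stop is one of two readings and not a certainty. It does not settle the matter, because the protocol also uses the word management for drug actions: Table 18's title covers both columns, and Table 19's management column includes withholding and discontinuing RO7172508. Reading B also leaves the reversal in the steroid instructions at unequal grades.

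Three stronger conclusions are tempting and are not supported.

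- A reader might infer that a participant with a Grade 3-4 toxicity would in practice be kept on treatment. Sections 6.6, 7.1 and 8 make that unlikely, and an experienced investigator may well not follow the sentence literally.
- A reader might infer that DLT coding, and so the MTD, is affected, since Section 4.1.3.1 says "Failure to recover from any RO7172508-related toxicity that results in a dose-delay of more than 14 days (any regimen) is defined as a DLT" and excepts certain hepatic events that recover within a week. In non-fractionated Q3W dosing no dose falls due in that week, so a hold cannot change recovery within it. The hepatic exception is limited to Grade 3 events in participants with liver lesions, starting within 24 hours of infusion. A clinically significant hepatic Grade 4 event, or a Grade 3 event that has not recovered in a week, meets the DLT definition whatever Table 18 says. What remains is a possible effect of steroids on recovery time or of holds on accrued delay, and the documents give nothing with which to size it.
- A reader might infer that discontinuation rates would not be comparable between doses. The documents give no frequency of concurrent events, by dose or overall.

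**Conclusion.** The sentence is wrong as written, because it contradicts Table 18 under either reading whenever the other-organ toxicity is sufficiently more severe than the respiratory one. On the wider reading 7 of 12 grade combinations are affected, 3 outright and 4 only when a Grade ≥3 event lasts at least 5 days. On the narrower reading the drug actions are intact, and the conflict is confined to IV steroids for other-organ Grade 3-4 events with respiratory Grade 1 or 2.

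These counts describe the table and not expected patients. They rest on reading the other-organ Grade 3 action as also covering Grade 4, and on both events being attributed to tumor inflammation. The override was probably not intended: the stricter other-organ action is marked in italics as new in the current version, whereas the precedence sentence is not. The text itself does not say so. The point concerns patient safety and consistent instructions to sites. It makes no claim about the MTD or about comparisons between doses.

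**What to change.** Reconcile the 8.3.8.2 sentence with Table 18. The revised text should state:

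1. whether the sentence governs the initial-management column, the column on action with RO7172508, or both;
2. how it applies when the respiratory and other-organ toxicities differ in grade;
3. whether the clause on Grade ≥3 toxicity lasting at least 5 days still applies when a respiratory toxicity is present.

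Whatever is chosen, the presence of a second toxicity should not change the instruction for the first by accident. The sponsor's clinical team chooses the rule, and none is proposed here. The cost is one sentence in 8.3.8.2 and a note to Table 18 at the next amendment, with no additional data or participants.
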